15.4 Analysis Plan Including Plans for Formal Interim Analysis

Both short term and long term toxic effects of therapy will be captured and monitored closely. Severe toxic events will be reported and monitored as per NCI guidelines for clinical studies (e.g., CTEP-AERS). These data will be critical in the assessment of each of the treatment regimens. In addition, the Alliance DSMB will perform a formal review of the available data at each of its semiannual meetings. This review will include both acute and late toxicity.

After discontinuing one of the experimental arms with worse toxicity profile, in the second stage of the study, the first formal interim analysis for efficacy will occur once 78 deaths are observed in the remaining study arms. After that, formal interim analyses will be conducted annually, with the final analysis at year 8.5, corresponding to approximately 140, 213, 292, 374, 437 and 483 deaths. The trial is subject to stopping early for either superiority or inferiority of the experimental relative to the standard arm if either arm was markedly superior in terms of overall survival. The main reason is that if both arms were roughly equal in terms of overall survival, the final conclusion might be to recommend the experimental arm for future use because of less toxicity or more convenience. Using S+SeqTrial [83], we will construct two-sided symmetric monitoring boundaries in the spirit of O'Brien and Fleming [84]. To maintain overall 1-sided alpha level of 0.025 for each boundary and be conservative in the initial looks, we will truncate alpha level at 0.0005 for the first look and at 0.0025 for other interim looks [85]. The final analysis at 8.5 years after study activation will conclude superiority (inferiority) of the remaining experimental arm to the standard arm if the p-value of a one-sided log rank test for superiority (inferiority) is less than 0.0220. The following table displays the operating characteristics, including power, average study size, stopping probabilities under true hazard ratios of 0.75, 1.0, 1.3, and 1.5. The exact performance of the study design, especially under different allocation ratios in the first and the second stage of the study, will be investigated using simulation.

Hazard Ratio ($\lambda_1/\lambda_{2/3}$)	Expected Number of Deaths	Prob. to Reject $H_0: \lambda_1 / \lambda_{2/3} = 1$ (Power)	Early Stop Prob. for Superiority	Early Stop Prob. for Inferiority
0.75	354	0.8763	0.0000	0.6348
1.0	479	0.0250	0.0081	0.0081
1.3	377	0.8106	0.5357	0.0000
1.5	245	0.9928	0.9385	0.0000

The Alliance DSMB will review the data available from the trial at each of its semiannual meetings. This will include toxicity, disease recurrence and survival information. The DSMB will determine which of its biannual meetings most appropriately fits the protocol-dictated one-year formal interim analysis. This determination will be based on a recommendation of the study statistician. In determining whether the trial should be continued, the DSMB will consider the results at each interim analysis, as described above. The DSMB will use its discretion in weighing the combined impact of treatment-related morbidity, disease recurrence and overall survival.

Overall survival (OS) is defined as the time between randomization and death from all causes. Overall survival curve will be estimated by the Kaplan-Meier method. The primary analysis is to test the survival benefit of the experimental therapy over the standard therapy using stratified log rank test in the intent-to-treat (ITT) population. Six stratification factors, including Gender, Weight loss, ECOG Performance Status, Radiotherapy Technique, Radiotherapy Start Time, and Chemotherapy Backbone, have been used in randomization. As a total of 144 stratum have been defined by these factors and many of the stratum may end up of small number of patients. For the primary analysis, the stratified log rank test will only stratify on patient subgroups defined by Performance Status (0 vs 1/2) and Chemotherapy Choice (entry prior to the option to use carboplatin, choice of carboplatin among those patients for which this is an option, and choice of cisplatin among those patients for which this is an option). Cox's proportional hazards model will be used to estimate hazard ratio between treatments with and without adjusting for other prognostic factors.

Failure free survival (FFS) is the time from randomization to death of all causes or disease progression, whichever comes first. In this study, second primary tumors will not be viewed as disease progression. FFS will be analyzed in a similar manner to overall survival (OS).

The rates of local relapse, distant metastases and brain metastases with the regimens will be evaluated using logistic regression with treatment and other prognostic factors in the model.

Contingency tables will be used to summarize the frequency of toxicity by severity, type and treatment. For comparison of the frequency of toxic events, the Cochran-Mantel-Haenszel test will be used to take advantage of the trend effect among toxicity grades.

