15.3 Sample Size with Power Justification

This randomized phase III study is to determine the efficacy of 70 Day QD RT (arm 2) or 61.2 Gy concurrent boost RT (arm 3) as compared to the standard therapy 45 Gy BID RT (arm 1) in patients with limited small cell lung cancer. The primary endpoint is overall survival, which is measured from the date of randomization to the date of death from any cause.

The implementation of the study will be divided into two stages. In the first stage, eligible patients will be randomized with a 1:1:1 allocation to arm 1, 2 and 3. The toxicity profiles of two experimental arms (arm 2 and arm 3) will be analyzed after 30 patients have been treated to each of the experimental arms. If no statistically significant difference of adverse events is found between experimental arms, additional 20 patients will be treated by each experimental arm. The pattern will be repeated until a significant difference is found or 70 patients have been treated by each experimental arm, whichever comes first. In the second stage, after the decision of dropping the experimental arm with higher toxicity is made, the study will continue with two remaining arms with 1:1 allocation. All randomization will be made using a permuted-block scheme, stratified by gender (female vs. male), ECOG PS (0 vs. 1 vs. 2), weight loss within 6 months before entry (weight loss $\leq 5\%$ vs. $> 5\%$), radiotherapy technique: IMRT vs. 3D, timing of first chemotherapy treatment (prior to randomization vs. post-randomization with the start of radiotherapy on the first cycle vs. post randomization with the start of radiotherapy on the second cycle), and chemotherapy backbone (carboplatin vs. cisplatin) [82]. In the end, the study will

randomize 303 patients to arm 1, 303 to Arm 2 and 30-70 patients to the discontinued experimental arm. As of November 20, 2012, the discontinued experimental arm (Arm 3) randomized 88 patients due to a delayed final toxicity interim decision. With an allowance of 5% of patients canceling or ineligible for randomization, the study will accrue a total of 729 patients over a period of 6 years at about 10 patients per month. All randomized patients will be followed for at least 2.5 years after enrollment

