The trial is designed to have adequate power to test the null hypothesis $H_0: \log(\lambda_1 / \lambda_{2/3}) = 0$ versus the alternative hypothesis $H_a: \log(\lambda_1 / \lambda_{2/3}) \geq 1.3$ for the comparison of overall survival between the remaining experimental arm (arm 2) and the standard arm (arm 1). The power analysis is based on the following assumptions: (1) the 2-year overall survival rate of the remaining experimental arm (arm 2) is 57.3% and that of arm A is 48.5%. Under exponential survival distribution, the median survival for the remaining experimental arm is 29.9 months and for the standard arm is 23 months, or a hazard ratio of 1.3 (λ_1 / λ_2) for the standard arm to the remaining experimental arm; (2) an accrual length of 6 years; (3) 303 eligible patients in the standard arm and 303 eligible patients in the remaining experimental arm; (4) additional follow-up of 2.5 years after the last enrollment; (5) a two-sided significance level of 0.05. Under these assumptions, at the time of final analysis, at least 483 deaths are anticipated under alternative hypotheses for the two remaining comparative arms. Without taking into account the expected minimal loss of power due to interim analyses, the power in detecting the survival improvement for the remaining experimental arm (arm 2) as compared to the standard arm is at least 81.9% using a stratified log-rank test.

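### The final overall-survival test is fixed at 8.5 years after activation, but the stated 483 deaths and 81% power hold at that date only if accrual ends by year 6, and the documents show that it ran longer

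*Combined protocol and SAP*

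**What the plan says.** Section 15.4 names year 8.5 twice. The schedule of looks reads: "formal interim analyses will be conducted annually, with the final analysis at year 8.5, corresponding to approximately 140, 213, 292, 374, 437 and 483 deaths". Its decision rule reads: "The final analysis at 8.5 years after study activation will conclude superiority (inferiority) of the remaining experimental arm to the standard arm". This applies when the one-sided log-rank p-value is below 0.0220. Only the first efficacy look is triggered by deaths: "the first formal interim analysis for efficacy will occur once 78 deaths are observed in the remaining study arms".

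Section 15.3 gives the assumptions behind the power. They are 303 eligible patients per arm, exponential survival with medians of 23 and 29.9 months, 6 years of accrual and "additional follow-up of 2.5 years after the last enrollment". Under these, "at the time of final analysis, at least 483 deaths are anticipated under alternative hypotheses". The stated power is 81.9% before allowing for interim looks and 0.8106 in the Section 15.4 table. Section 15.3 also says "All randomized patients will be followed for at least 2.5 years after enrollment" and "the study will accrue a total of 729 patients over a period of 6 years at about 10 patients per month". Section 15.5 repeats the 6-year accrual.

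Neither section says what happens to the date of the final test, or to the 0.0220 cut, if accrual takes longer.

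**The concern.** Year 8.5 equals 6 + 2.5, so the date, the follow-up and the death count describe one moment only while accrual lasts 6 years. If enrollment runs past year 6 and the date stays fixed, late entrants contribute little follow-up and the primary test is made with fewer deaths than its power requires.

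The documents indicate that this happened:

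- Section 1.2 records an amendment on 15 September 2009.
- Section 15.3 states: "As of November 20, 2012, the discontinued experimental arm (Arm 3) randomized 88 patients".
- Section 5.6 says quality-of-life accrual was met on 30 August 2017, and that those patients are registered to the companion study and the main trial together.
- Section 6.1 carries a March 2018 date, while Section 5.4 still instructs sites how to enroll.

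A trial that follows the rule literally would miss the power it states. A trial that departs from it would be choosing a new date after interim survival results exist, with no rule set in advance.

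**Working it through.** **Inputs.** From Sections 15.3 and 15.4: 303 per arm; medians 23 and 29.9 months; hazard ratio 1.3; final one-sided cut 0.0220 (z = 2.014). Hazards are λ = ln 2/median = 0.03014 and 0.02318 per month.

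**Formulas.** With enrollment at rate r per arm from month a to month b (b capped at t), expected deaths by month t are r[(b − a) − (exp(−λ(t − b)) − exp(−λ(t − a)))/λ], summed over segments and arms, with no loss to follow-up. Single-test power with d deaths is Φ(ln 1.3 × √d/2 − 2.014).

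**Reproducing the plan.** With r = 303/72 over 72 months and t = 102, the standard arm gives 4.208 × (72 − 11.90) = 252.9 and the experimental arm 4.208 × (72 − 17.46) = 229.5. The total is 482.4, against 483 stated. At years 2.5, 3.5, ..., 8.5 the totals are 78, 140, 213, 293, 375, 437 and 482, against 78, 140, 213, 292, 374, 437 and 483. The listed counts are therefore a calendar projection of 6-year accrual. At 483 deaths power is 82.2% at one-sided 0.025 (81.9% stated) and 80.8% at 0.0220.

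**Did accrual pass 6 years?** For 30 August 2017 to fall within 6 years, activation could be no earlier than 30 August 2011, which is 14.7 months before 20 November 2012. If 1:1:1 allocation put 88 patients in each of three arms by then, 264/14.7 = 18 per month would have been needed, against 10 planned. The September 2009 amendment also points to an earlier start.

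**Like-for-like baseline.** Take 6 years of accrual at a constant total rate, with 88 per arm at 1:1:1 and then 215 per arm at 1:1. This gives 473.4 deaths at year 8.5 and 80.0% power. About 9 of the missing deaths (482.4 − 473.4) thus come from the three-arm stage, not from the date.

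**Scenarios.** Assumed: 88 in each of arms A and B by 20 November 2012, and the remaining 215 per arm enrolled evenly to the end date. Activation is either 15 September 2009 (38.2 months earlier) or about September 2010 (264 patients at 10 per month = 26.4 months earlier).

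| Activation | Enrollment ends | Accrual, months | Deaths at year 8.5 | Power | Last patient's follow-up at year 8.5 | 483 deaths expected at |
|---|---|---|---|---|---|---|
| Sept 2009 | 30 Aug 2017 | 95.5 | 399 | 73% | 6.5 months | year 10.2 |
| Sept 2009 | mid-Mar 2018 | 101.9 | 378 | 70% | about 0 | year 10.5 |
| Sept 2010 | 30 Aug 2017 | 83.7 | 452 | 78% | 18.3 months | year 9.2 |
| Sept 2010 | mid-Mar 2018 | 90.2 | 436 | 77% | 11.8 months | year 9.5 |

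Against the baseline, the calendar rule costs 473.4 − 451.6 = 22 to 473.4 − 377.6 = 96 deaths, and 80.0 − 78.0 = 2 to 80.0 − 70.4 = 10 points of power.

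**Type I error.** Recursive integration used information proportional to deaths, cuts of 0.0005 at the first look and 0.0025 at later interim looks, and 0.0220 at year 8.5. It gives 0.0246 to 0.0253 per side.

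**The case against.** The strongest reply is that the plan is not ambiguous. Section 15.4 puts year 8.5 in the decision rule, 483 is an anticipated count and 2.5 years is a power assumption. This stands. A reader might infer three competing triggers with none in charge, but the text does not support that. The difficulty is that the one rule stated rests on an accrual period that no longer holds.

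A reader might also infer that an early test breaks the follow-up commitment. It does not. Section 15.3 promises follow-up, not that the analysis waits for it, and Section 7.0 continues follow-up well beyond. What is true is that some patients would have less than 2.5 years of follow-up at the test.

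Nor do the documents support a claim of inflated type I error, as the check shows. Larger power losses follow if enrollment is assumed to run well past March 2018, but nothing in the text dates its end.

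The size is open to challenge too. Neither the activation date nor the end of accrual is given. September 2010 is a favorable assumption that sits awkwardly with a 2009 amendment. Enrollment concentrated early in the second stage would shrink the loss.

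Finally, a calendar rule always reports, whereas a bare 483-death trigger might not. It needs 483/606 = 80% of patients to die. The exponential model implies exp(−60 × 0.03014) = 16% alive at 5 years on 45 Gy twice daily, while Section 1.1 reports 26% for that regimen. With assumed long-term plateaus of 20% and 25%, deaths could not exceed 303 × 0.80 + 303 × 0.75 = 470. This stands, and the fix must allow for it.

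**Conclusion.** The concern holds as a mismatch between the fixed date and the power claimed for it. Applied as written after the accrual that the documents indicate, the primary test would have about 378 to 452 deaths and 70% to 78% power, against the stated 483 and 81%. Of that shortfall, about 2 to 10 points are due to the date. These figures rest on the assumed activation dates, even accrual after November 2012, exponential survival, and accrual ends tied to dates in the text. The plan's own arithmetic is sound under its assumptions. It should be corrected because it affects the primary analysis and the change is cheap.

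**What to change.** In Section 15.4, replace both year-8.5 statements with a final analysis at 483 deaths in arms A and B or at a calendar backstop, whichever comes first. Set the backstop in advance relative to last enrollment, and no earlier than 2.5 years after it. State that the final critical value is recomputed at the deaths actually observed, given the interim looks already taken, to hold 0.025 per side. Update the 6-year accrual assumption in Sections 15.3 and 15.5, and give the expected deaths and power if the backstop applies. Make the change, and record that it was made, without reference to comparative survival results.

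The main cost is time. Under the four scenarios 483 deaths arrive at about year 9.2 to 10.5, shortly before 2.5 years after last enrollment (year 9.5 to 11.0, with about 492 to 502 deaths). The test would come later if survival plateaus and the backstop applies. Continuing the annual looks can add one or two looks. Leaving 0.0220 unchanged would then give about 0.026 per side. The recomputed cut would be near 0.021, with power still about 81% at 483 deaths. These cuts illustrate the cost and are not proposed as fixed values.

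### The final cut-off of 0.0220 in Section 15.4 gives a one-sided error of 0.0253 on the plan's own looks; about 0.0217 holds the stated 0.025 and agrees with the plan's table

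*Combined protocol and SAP*

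**What the plan says.** All the design inputs are in Section 15.4.

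- **Overall level:** "To maintain overall 1-sided alpha level of 0.025 for each boundary", with two-sided symmetric boundaries.
- **Interim levels:** "we will truncate alpha level at 0.0005 for the first look and at 0.0025 for other interim looks".
- **Looks:** "the first formal interim analysis for efficacy will occur once 78 deaths are observed in the remaining study arms". The later looks are annual, "corresponding to approximately 140, 213, 292, 374, 437 and 483 deaths". That makes six interim looks and a final analysis.
- **Timing of the final analysis:** "formal interim analyses will be conducted annually, with the final analysis at year 8.5".
- **Final decision rule:** success or failure is declared "if the p-value of a one-sided log rank test for superiority (inferiority) is less than 0.0220".

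The table in the same section gives a rejection probability of 0.0250 at a hazard ratio of 1.0, of which 0.0081 is early stopping on each side. It gives power of 0.8763, 0.8106 and 0.9928 at hazard ratios of 0.75, 1.3 and 1.5. The section adds that exact performance will be studied by simulation. It does not say that the final cut-off would be recalculated from the looks held.

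**The concern.** The interim levels, the death counts, the final level and the total error are tied together: once three are fixed, the fourth follows. The plan prints all four, and they do not agree. The number that is off is the decision threshold for the primary endpoint. A final p-value that met the printed cut-off but not the level needed for 0.025 would be declared significant while the stated error rate was exceeded. The plan would then give two answers, one from its text and one from its table.

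**Working it through.** **Model.** Let D_k be the deaths at look k and θ the log hazard ratio. With 1:1 allocation the log-rank score is approximately normal with mean θ·D_k/4 and variance D_k/4, with independent increments. The correlation between the statistics at looks j < k is √(D_j/D_k). Boundaries are symmetric, and crossing probabilities come from recursive numerical integration.

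**Step 1: the fixed-sample power in Section 15.3.** Power = Φ(√(483/4)·ln 1.3 − 1.960) = Φ(10.989 × 0.2624 − 1.960) = Φ(0.923) = 0.822. The plan says at least 81.9%, so the model is suitable.

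**Step 2: boundaries.** One-sided 0.0005 is z = 3.291, 0.0025 is z = 2.807, and 0.0220 is z = 2.014.

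**Step 3: error under no difference.** Probability of first crossing the upper boundary at each look:

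| Deaths | Level | First crossing |
|---|---|---|
| 78 | 0.0005 | 0.000500 |
| 140 | 0.0025 | 0.002295 |
| 213 | 0.0025 | 0.001688 |
| 292 | 0.0025 | 0.001418 |
| 374 | 0.0025 | 0.001221 |
| 437 | 0.0025 | 0.000937 |
| 483 | 0.0220 | 0.017216 |

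The six interim looks sum to 0.00806, which is the table's 0.0081. Adding the final look gives 0.00806 + 0.01722 = 0.0253 one-sided; doubled, 2 × 0.025275 = 0.05055. A simulation of 4 million trials gave 0.0252 (standard error 0.0001).

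**Step 4: comparison with the table, and the level that fits.** Solving for a total of 0.0250 gives a final level of 0.0217 (z = 2.020).

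| Quantity | Table | Final 0.0220 | Final 0.0217 |
|---|---|---|---|
| Early stop, HR 1.0 (each side) | 0.0081 | 0.0081 | 0.0081 |
| Early stop, HR 1.3 (superiority) | 0.5357 | 0.5356 | 0.5356 |
| Early stop, HR 0.75 (inferiority) | 0.6348 | 0.6347 | 0.6347 |
| Early stop, HR 1.5 (superiority) | 0.9385 | 0.9384 | 0.9384 |
| Total, HR 1.0 | 0.0250 | 0.0253 | 0.0250 |
| Power, HR 1.3 | 0.8106 | 0.8124 | 0.8110 |
| Power, HR 0.75 | 0.8763 | 0.8778 | 0.8767 |

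The early-stopping rows do not depend on the final cut-off, and they agree. The last three rows do depend on it. They miss with 0.0220 and move to, or close to, the table with 0.0217.

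**Step 5: could the inputs explain the gap?**

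- Shifting each death count by up to 3 leaves the total at 0.0252 to 0.0253.
- Removing the lower boundary also gives 0.0253.
- If truncation means O'Brien-Fleming levels capped at 0.0005 and 0.0025, the total is 0.0231, but early stopping is 0.0053.
- If it means O'Brien-Fleming levels raised to at least those values, the total is 0.0291 and early stopping is 0.0203.

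Only flat levels of 0.0005 and then 0.0025 give the table's 0.0081.

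**The case against.** The strongest objection is size. The excess is 0.0003 one-sided, the log-rank test is itself used through a normal approximation, and the death counts are labelled approximate. The overall level, the interim levels and the table agree with one another, so 0.0220 may be a rounding or transcription slip; the documents do not say. All of this stands, and it makes the point a small one. It does not remove the disagreement: a threshold printed to four decimals should give the level the plan states, and the approximate death counts do not close the gap. The promised simulation does not commit the plan to changing the cut-off.

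A reader might infer something stronger: that accrual was visibly slow, that annual looks at 0.0025 would therefore accumulate, and that the error with 0.0220 would reach about 0.026. The documents do not support this as a finding.

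- Section 15.4 sets the final analysis by the calendar, at 8.5 years after activation. Take 606 patients, the plan's exponential medians, uniform accrual and annual looks from 78 deaths (omitting any within 3 months of the final). With the final analysis at 102 months, the error with 0.0220 is 0.0253, 0.0253, 0.0252, 0.0249 and 0.0247 for accrual over 72, 84, 96, 108 and 120 months. Under the written rule, slower accrual does not add interim looks, and the error does not rise materially.
- The pace is inferred. No activation date or accrual curve is given. The one count, "As of November 20, 2012, the discontinued experimental arm (Arm 3) randomized 88 patients", concerns the discontinued arm.

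**Conclusion.** The point holds and is small. On the plan's own looks and interim levels, 0.0220 gives 0.0253 one-sided against the stated 0.025 and the tabulated 0.0250; the level needed is about 0.0217. On the planned schedule the affected final p-values lie between 0.0217 and 0.0220. In terms of the observed hazard ratio at 483 deaths, the threshold moves from exp(2.014/10.989) = 1.201 to exp(2.020/10.989) = 1.202.

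This rests on the normal approximation to the log-rank score, information of one quarter of the deaths, and the flat reading of the interim levels, which is the only one of those tried that reproduces the table.

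An error of about 0.026 is conditional. It would arise only if the final analysis were delayed past year 8.5 to wait for 483 deaths, with seven or eight interim looks held first. In that case the calculation gives roughly 0.0257 to 0.0263. The plan states no such rule, so neither that figure nor a wider p-value window starting near 0.021 should be attributed to the plan as written.

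**What to change.** In Section 15.4, replace 0.0220 with 0.0217 for the planned schedule. Add one sentence: the final critical value will be computed from the joint distribution of the looks actually held, at their actual death counts, so that total one-sided error for each boundary is 0.025. The added sentence is useful in any case, because the section lets the DSMB choose which of its meetings serves as each annual look, so the actual death counts will differ from those listed. It would also cover a delayed final analysis, should one occur.

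The cost is one number, one sentence and a short boundary calculation at the final analysis. Power at a hazard ratio of 1.3 goes from 81.2% to 81.1%. The sample size, the interim looks and the table do not change.
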